### **Study aim**

The ultimate goal is to create a follow up study with the intention to intervene or optimize those risk factors, identified by this current study, possibly leading to a reduction of CAL.

### 3. STUDY DESIGN

The Leakage Check procedure will use perioperative risk factors identified in a systematic review. The Leakage Check procedure will be developed in a format that is already accepted and applied in the operating room before the start of the operation. Preoperative risk factors will be screened prior to the operation. This will be done by using the colon leakage score. Informed consent is requested prior to the operation.

The Leakage Check procedure is a multifactorial checklist that is scored with the whole surgical team prior to a surgical procedure. For this study a colorectal checklist has been designed, that will be scored during surgery prior to the creation of an anastomosis. The checklist is carried out by a member of the operation team. The checklist will also be offered through a website to minimize the registration burden in other hospitals. The checklist contains five main general topics; general condition, perfusion, contamination and visibility of the surgical field and surgery related factors. For each topic a number of parameters and inquiries are required to be answered.

This study is a multicentre observational cohort study with gradual introduction of the protocol (see Table 1) over the participating hospitals. At the moment there is participation of seventeen hospitals in the Netherlands. The reason being that there is a large group of anastomotic procedure outcomes without perioperative monitoring necessary that can be used to compare the Leakage Check procedure results with. To test the hypothesis, that even only keeping track of the risk factors a reduction of CAL occurs, a prospective group without perioperative monitoring is required as zero group. January 2016 is the starting point (T0) of the first hospital with the Leakage Check procedure, three months later the second hospital starts with implementing the Leakage Check procedure.

Table 1. Gradual introduction. **T**: number of months from start point till implementing a Leakage Check procedure . **Green columns**: Using a Leakage Check. **Red columns**: Not using a Leakage Check.

MMC T:0	
VUMC	T:3
To be determined	T:6
To be determined	T:9
To be determined	

In every participating hospital one individual has been designated to determine which patients are included. Every week scheduled patients for colorectal surgery with anastomosis will be selected by one local colorectal surgeon in the VUMC and MMC. Hopefully almost all operations with anastomosis will be enrolled in our study, since there is no difference in treatment or potential damage. This must also be communicated to one main individual in the VUMC ([name]) to create a good overview of the scheduled Leakage Check procedure. The performing surgeon requests to apply the questionnaire at the moment before constructing the anastomosis. The anesthetist, operating room nurses and other relevant team members in the operating room (OR) will be asked to participate in this procedure. The questionnaire is found on the website [www.naadlekkage.nl](http://www.naadlekkage.nl). Every participating hospital has an own account on this website. Data following this procedure will be securely collected in a prospective online database. Patient characteristics, laboratory, pathologic, radiologic, hemodynamic and surgery related items will be scored and added. In order to obtain reliability of the results, the Leakage Check procedures that have been completed in more than 90% will only be taken into account.

Before starting with the execution of the Leakage Check procedure, the research will be announced to all predicted partici employees.

Important preoperative factors as well as postoperative complications need to be monitored. For every Leak Check patient, it is necessary to fill in a two pages' questionnaire with preoperative and postoperative outcome information. It is important that all CAL cases are diagnosed in accordance with the guidelines. It is necessary to comply with the definition of Reisinger in order to be reckoned as CAL. The definition of anastomotic leakage is: "Clinically relevant anastomotic leakage was defined as extraluminal presence of contrast fluid on contrast-enhanced CT scans and/or leakage when relaparotomy was performed, requiring reintervention. Indications for CT or relaparotomy were based on clinical presentation, including fever, tachycardia, tachypnea, low saturation, low urinary production, abdominal pain, and signs of ileus or gastric retention."

Statistics are used to calculate a possible difference between patient outcomes and deviations in perioperative parameters, by means of a chi-squared test. The patients are divided into two groups, with and without CAL complication. The final purpose of this study is to optimize the risk factors in a follow up study. The determined perioperative risk factors will be ascribed optimum values by using the results of the Leak Check-Study. Dividing the patients into leaking and non-leaking groups to determine the most average values for perioperative factors. These results can be compared with the so-called optimal values from the literature of the systematic review. From these results, a new Leakage Check questionnaire will be designed for in the follow up study, containing often aberrant and modifiable perioperative factors and their optimal range. It depends on the obtained results how the optimization will take place.

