## 4. STUDY POPULATION

### 4.1 Population

The intended population for this study consists of all consecutive adult patients undergoing colorectal surgery with anastomosis for benign as well as malign cause and treated at the participating centers.

The intended population for this study consists of 2000 adult patients undergoing colorectal surgery with anastomosis for benign as well as malign cause.

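### The protocol does not require outcome data for consented patients whose check is not called in theatre, so the counted monitored group may be selected by an intraoperative decision

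*Protocol*

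**What the plan says.** All of the operative text is in protocol section 3 (Study design).

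- **Trigger.** "The performing surgeon requests to apply the questionnaire at the moment before constructing the anastomosis".
- **Follow-up form.** "For every Leak Check patient, it is necessary to fill in a two pages' questionnaire with preoperative and postoperative outcome information". The protocol does not say whether a Leak Check patient is one enrolled or scheduled for the check, or one in whom it was carried out.
- **Counting rule.** "the Leakage Check procedures that have been completed in more than 90% will only be taken into account".
- **Coverage.** "Hopefully almost all operations with anastomosis will be enrolled in our study". No target is set, and no count of checks not done is asked for.
- **Log.** Scheduled cases are reported centrally "to create a good overview of the scheduled Leakage Check procedure".

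Section 4.1 gives the intended population as "all consecutive adult patients undergoing colorectal surgery with anastomosis for benign as well as malign cause and treated at the participating centers". Section 5.3 provides for withdrawal by the participant before surgery, and by the investigator when no anastomosis is made. A check that was not done is neither of these.

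Section 3 also calls for a prospective unmonitored zero group, against which a possible reduction in leakage is judged (secondary objective 4 in section 2). Section 5.1.2 makes the feasibility of scoring the checklist during surgery a secondary parameter.

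**The concern.** Consent is obtained before the operation, but whether a check exists is settled during it, by someone who can see how the operation is going. If the check is passed over, the patient still has an anastomosis and can still leak. No sentence expressly requires that patient's outcome form or a reason for the omission, and the counting rule leaves the patient out of the monitored data.

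Two results depend on this:

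- **Secondary objective 4.** The zero group consists of patients operated on without the check, so no request in theatre decides who belongs to it. The monitored group, if it consists of counted checks, has been filtered by that request. Any link between skipping and leak risk then shows up as a difference between the groups, even if monitoring has no effect.
- **Feasibility.** The clearest failure of feasibility is a check that was never started. If only started checks are recorded, the parameter is estimated among the successes.

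The primary risk-factor analysis is affected differently. Patients without a check have no checklist values at all. What is at stake there is knowing how many patients and leaks the analysis omits.

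**Working it through.** **Step 1: follow one patient through the text.** Take a consented patient who receives an anastomosis and whose check is not called.

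| Provision | Effect on this patient |
|---|---|
| Section 4.1, population | Belongs to the intended population |
| Section 5.3, withdrawal | Not withdrawn |
| Section 3, two-page form | Required only if *Leak Check patient* means enrolled or scheduled; not required if it means check performed |
| Section 3, 90% rule | No items completed, so not among the counted checks |
| Section 3, overview | Can appear as scheduled; no instruction to compare with checks performed |

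The form is uncertain because of an undefined term. Exclusion from the counted checks follows on either reading.

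**Step 2: possible size.** The protocol states no figure for skipped checks, so there is nothing to reproduce. The inputs are:

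- True leak rate L among all consented patients after roll-out: 8%, the lower end of the 8–13% incidence in the Summary and section 1. Monitoring is taken to have no effect.
- Share skipped s: 10% or 20% (assumption).
- Leak rate in skipped patients q: 8% to 14% (assumption).

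The rate in checked patients is (L − s × q) / (1 − s).

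| s | q | Checked group | Relative change from 8% |
|---|---|---|---|
| 10% | 8% | (8 − 0.8)/0.9 = 8.0% | 0 |
| 10% | 14% | (8 − 1.4)/0.9 = 7.33% | −8% |
| 20% | 8% | (8 − 1.6)/0.8 = 8.0% | 0 |
| 20% | 10% | (8 − 2.0)/0.8 = 7.5% | −6% |
| 20% | 14% | (8 − 2.8)/0.8 = 6.5% | −19% |

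**Step 3: direction.** If the check is passed over in quick, uncomplicated operations, q lies below 8%. As an illustration, take q = 2%, the rate section 4.4 assumes without deviating factors. The checked group then shows (8 − 0.2)/0.9 = 8.67% with 10% skipped and (8 − 0.4)/0.8 = 9.5% with 20% skipped. The same mechanism would then hide a real benefit.

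**Step 4: leaks left out.** Per 1,000 consented patients there are 80 leaks. With 20% skipped, 200 × 8% = 16 of them are uncounted at equal risk, and 200 × 14% = 28 at the upper assumption. Leaks are lost even where the rate is unbiased.

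**Step 5: effect on a test.** Assume 1,000 unmonitored patients at 8% and 800 checked patients, with 20% skipped at twice the risk of checked patients. The checked rate is 8/(0.8 + 0.2 × 2) = 6.67%, and the skipped rate is 13.3%. The difference is 1.33 percentage points, with a standard error of 1.24 points under the null (pooled rate 7.41%) and 1.23 points under the alternative. The probability of a significant reduction at two-sided 0.05 is Φ[(1.33 − 1.96 × 1.24)/1.23], about 19%. It should be 2.5% in that direction. Patients are treated as independent and hospital effects are ignored.

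**The case against.** A reader might infer that outcomes are collected only when the surgeon calls the check, and that skipped patients vanish without trace. The documents do not say this:

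- The sentence on the surgeon's request says who starts the check and when. It does not make the check optional.
- *Leak Check patient* can be read as enrolled or scheduled.
- Section 3 has preoperative factors screened before the operation and lists preoperative, intraoperative and postoperative data separately.
- Section 5.3 does not remove the patient from the study.
- The overview of scheduled checks could identify the patient.

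These points stand, and the finding is therefore a missing requirement and not a stated exclusion from follow-up. Two passages do lean towards the narrower reading. Section 3 uses Leak Check for the intraoperative data, and section 6.2 awards authorship by the number of Leak Checks delivered. Neither settles the matter.

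It can also be said that Table 1 already assigns exposure by hospital and calendar time, so a comparison of checked patients only is not prescribed. That is fair as to the design. But the 90% rule carries no exception for this comparison, and no sentence says that post-roll-out patients without a counted check are retained.

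Finally, skip rates and leak rates in skipped patients are assumed, and zero or reversed bias is possible. That is correct and is shown in the working. The point also overlaps with the 90% rule, since that rule is what keeps an unperformed check out of the count. Even so, a more lenient threshold would not bring in a patient with no check.

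**Conclusion.** The concern holds as a gap in required data collection together with a counting rule. The protocol leaves *Leak Check patient* undefined and does not expressly require outcome data when a consented patient has an anastomosis but no check. The 90% rule leaves such patients out of the counted monitored group, against the intention to study "all consecutive adult patients undergoing colorectal surgery with anastomosis". The comparison for secondary objective 4 can be biased as a result, and feasibility can be assessed without its failures.

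Neither the size nor the direction of bias can be derived from the document. Under the assumptions in the working (8% true rate, 10–20% skipped, 8–14% leakage in skipped patients), the checked group shows 8.0% down to 6.5%, a spurious relative reduction of 0 to 19%. The sign reverses if easy operations are the ones skipped.

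This is not a matter to leave to an analysis plan, because leak status that was never collected cannot be recovered by analysis. The change is worth making; its main benefit is to secondary objective 4 and feasibility, not to the primary risk-factor analysis.

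**What to change.** 1. In section 3, require the two-page form for every consented patient who receives an anastomosis, whether or not the check was performed. This also removes the need to interpret *Leak Check patient*.
2. Add one field: check performed, yes or no, with the reason if no.
3. For secondary objective 4, classify all these patients by hospital phase (before or after that hospital's start), and not by whether a check exists or is more than 90% complete.
4. Use the overview of scheduled checks as the denominator for feasibility, and reconcile it with the checks performed.

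The cost is the existing form for some additional patients who have already consented, plus one field: a small amount of extra registration work at the sites. The scheduled list already exists, and clinical management is unchanged. The fix does not supply missing checklist values for the primary risk-factor analysis, but it shows how many patients and leaks that analysis omits.

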## 5. METHODS

## 5.1 Study parameters/endpoints

### 5.1.1 Main study parameter/endpoint

Main parameter is number of CAL patients with deviating perioperative risk factors.

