### 5.1.2 Secondary study parameters

Secondary parameters are number of deviating risk factors in total and feasibility of scoring a checklist during surgery.

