### **5.3 Withdrawal of individual subjects**

Only applicable if participants decide to withdraw before surgery. The investigator can decide to withdraw a subject from the study if the patient ends up not receiving an anastomosis.

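### Counting only Leakage Checks more than 90% complete is a post-enrolment filter: it discards recorded data, acts on one side of the zero-group comparison, and risks bias of unknown size and direction

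*Protocol*

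**What the plan says.** Protocol section 3 (Study design) gives the rule: "the Leakage Check procedures that have been completed in more than 90% will only be taken into account". The only reason offered is that it should make the findings reliable. No exception, sensitivity set, or comparison of counted with uncounted checklists is described.

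Other parts of the protocol bear on it:

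- Section 3 on timing: "Informed consent is requested prior to the operation". The checklist is scored during surgery, before the anastomosis is made.
- Section 4.1 on population: "all consecutive adult patients undergoing colorectal surgery with anastomosis".
- Section 5.3 on withdrawal: it covers patients who withdraw before surgery, and adds that "The investigator can decide to withdraw a subject from the study if the patient ends up not receiving an anastomosis". An incomplete checklist is not a ground.
- Section 5.1.1 on the endpoint: "Main parameter is number of CAL patients with deviating perioperative risk factors".
- Section 5.1.2 names as a secondary parameter the "feasibility of scoring a checklist during surgery", without a denominator.
- Section 2 (secondary objective 4) and section 3: leak rates under the Leakage Check are to be compared with a prospective zero group that has no perioperative monitoring.

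**The concern.** The rule selects on something observed after enrolment. A patient can meet every inclusion criterion, consent, receive an anastomosis, have glucose and MAP recorded, and still contribute nothing because other boxes were blank. Three analyses are exposed.

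1. **Risk factors.** The main parameter counts leak patients with deviating factors, so each leak patient whose checklist is not counted lowers it directly. Section 3 then derives optimum values for the follow-up study from the same patients, so any distortion carries forward.
2. **Monitoring comparison.** The zero group has no checklist, so the filter can act on the monitored side only. A difference in leak rate could arise from the filter alone.
3. **Feasibility.** If only counted checklists enter, every one is more than 90% complete by construction, whatever happened in theatre.

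What a protocol leaves to an analysis plan would not be a finding. This exclusion rule is fixed in the protocol itself.

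**Working it through.** The protocol gives no rate of item missingness and no expected loss, so there is no figure of its own to reproduce. What follows is illustration. The item count, missingness rates, risk ratios and retention rates are assumptions, except where a source is named.

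**How strict the threshold is.** Table 2 in section 5.2 reads as about 19 items: 5 general condition, 5 perfusion, 1 contamination and 8 surgery related. Its layout is damaged, so 18 to 20 is a fair range. With two blanks the completed share is 16/18 = 88.9%, 17/19 = 89.5% or 18/20 = 90.0%. None exceeds 90%, so at these counts one blank is tolerated and two are not. With 25 items two blanks would be tolerated (23/25 = 92%).

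**Checklists lost.** With m items, each missing independently with probability q, the share kept is P(X ≤ k), X ~ Binomial(m, q), where k = 1 for 18 to 20 items and k = 2 for 25 items.

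| Items | q = 2% | q = 5% | q = 10% |
|---|---|---|---|
| 18, kept | 0.950 | 0.774 | 0.450 |
| 19, kept | 0.945 | 0.755 | 0.420 |
| 20, kept | 0.940 | 0.736 | 0.392 |
| 25, kept | 0.987 | 0.873 | 0.537 |

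At 19 items about 5%, 25% or 58% is lost, so 2000 checklists become about 1891, 1509 or 841. At 25 items the loss is about 1%, 13% or 46%.

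**Effect on the monitored leak rate with no true effect.** Let p be the true rate, d the share dropped and R the leak risk of those dropped relative to those kept. The rate among those kept is p / [(1 − d) + dR]. Take p = 8%, the lower end of the incidence range in section 1, and d = 0.25:

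- R = 1.5: 0.08 / 1.125 = 7.1%
- R = 2: 0.08 / 1.25 = 6.4%

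Over the whole grid of losses above for 19 and 25 items, the result runs from 0.08 / (0.987 + 0.013 × 1.5) = 7.9% to 0.08 / (0.42 + 0.58 × 2) = 5.1%. If R is below 1 the shift goes the other way.

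**Effect on a risk-factor association.** Section 4.4 assumes 8% leakage with deviating factors and 2% without, a risk ratio of 4.0. Within each group the observed risk is p·r_L / [p·r_L + (1 − p)·r_N], where r_L and r_N are the retained shares of leak and non-leak patients.

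- Retention depends on deviation only (70% deviating, 90% not): the risks stay 8% and 2%, and the ratio stays 4.0. There is no bias.
- Deviating leak patients kept at 60%, deviating non-leak patients at 80%, all others at 90%: 0.048 / (0.048 + 0.736) = 6.1% against 2.0%, ratio 3.06.

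Bias therefore requires completeness to track leak risk beyond the factor being studied. The checklist is scored before the anastomosis exists, so the leak cannot itself cause a blank. Any link must run through shared causes such as the difficulty of the operation, or the centre.

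**The case against.** The strongest reply is that the harm is conjectural. The protocol reports no missingness and nothing linking it to leakage, and as shown above a filter related only to the deviation leaves the risk ratio intact. A reader might infer that the rule does bias the results, and in favour of the checklist. The documents do not support that; they support a risk of unknown size and direction. Urgency in particular is a weak mechanism. Patients come from weekly lists of scheduled operations (section 3), must be ASA 1 to 3 (section 4.2) and are consented across outpatient visits (section 7.2). Difficult operations remain a plausible route.

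A reader might also infer that the whole patient leaves the study. The sentence speaks of Leakage Check procedures, and postoperative outcomes come from a separate two-page questionnaire. Removal of the patient from the leak-rate comparison is a natural reading but not the only one. Equally, section 5.1.2 gives no denominator, so the feasibility parameter is not shown to be invalid; it is circular only if the rule governs it.

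The loss figures can be challenged too. The denominator may be larger than Table 2 suggests. Items are described as required, and some (hospital, elective operation, operation, anastomosis, stoma) would rarely be blank. With those five always filled, 5% missingness loses about 15% of 19-item checklists rather than 25%. Finally, section 4.2 calls the project exploratory, and the zero-group comparison serves a secondary objective.

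These points limit how firmly the consequences can be stated. They do not defend the rule: recorded values are discarded, the filter is one-sided in the zero-group comparison if it reaches that analysis, and nothing described would reveal whether it mattered.

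**Conclusion.** The point stands in a limited form. From the text alone, the rule is a post-enrolment filter, it is at odds with the consecutive population in section 4.1, it appears among neither the inclusion criteria nor the withdrawal grounds, and it cannot be applied to the zero group. It also discards data on the very parameter under test when other items are blank.

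Bias in the risk-factor associations or the monitored leak rate is a risk, conditional on completeness being related to leak risk beyond the factor studied. The losses of 5%, 25% or 58%, and the shift from 8.0% to 7.1% or 6.4%, show what the rule could do. They rest on assumed item counts, independent missingness and assumed risk ratios, and are not estimates for this study. The feasibility problem depends on whether the rule reaches that parameter, which the protocol should state.

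**What to change.** Amend section 3 and the matching parts of sections 5.1 and 6.1 as follows:

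- Remove completeness above 90% as a condition for analysis.
- Analyse each parameter in all enrolled patients with an anastomosis who have that item recorded, or use multiple imputation of missing items where a checklist was started. Checklists never started need not be imputed.
- Keep the >90% set as a sensitivity analysis, which preserves the stated aim of reliability.
- Compute the monitored-group leak rate in all enrolled patients for whom a check was due, regardless of completeness, so that no filter acts on one side only.
- Report feasibility as the share completed above 90% out of all due checklists.

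The cost is a wording change and modest analyst time; no additional data are collected. If imputation is chosen, it rests on a missing-at-random assumption, which should be stated.

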### **Secondary Objectives:**

2. Observe deviations of the parameters in the checklist during surgery.
3. Determine the extent of these parameters as risk factors of CAL.
4. Perceiving a possible reduction of CAL due to extra emphasizing of the hemodynamic factors.
5. Creating a profile identifying high risk patients perioperatively.
6. Increasing the awareness amongst surgeons of the influence of perioperative parameter changes for CAL.

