**Table 2. Leakage Check procedure**

General condition	Perfusion	Contamination and visibility	Surgery related factors
Temperature	Blood loss		Analgesia
Glucose	O 2 saturation	Contamination surgical field	Surgeon Fit to perform
Antibiotics	MAP		Elective operation Anastomose
Inotropic	Subjective rate of local perfusion		Operation Intra operative event\
Door movements	Fluid balance		Stoma Hospital

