## **6. STATISTICAL ANALYSIS**

### **6.1 Statistical plan**

Evaluation of relationships between parameters deviations and leakage rates of anastomosis. Analyses for outcome will be performed on the 2 groups, one with CAL and a group without CAL. Data will be analyzed with Statistical Package for the Social Sciences software version 20 (SPSS Inc., Chicago, IK, USA).

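### The only stated test for risk factors is an unadjusted chi-squared test in a mixed-case cohort, so a parameter that merely tracks case mix can be flagged and carried forward

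*Protocol*

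**What the plan says.** Protocol section 3 (Study design) states the method: "Statistics are used to calculate a possible difference between patient outcomes and deviations in perioperative parameters, by means of a chi-squared test". It continues: "The patients are divided into two groups, with and without CAL complication". Section 6.1 (Statistical plan) repeats the comparison, "Analyses for outcome will be performed on the 2 groups, one with CAL and a group without CAL", and otherwise names only the software. Neither section mentions a covariate, stratum, regression model, hospital term or multiplicity rule.

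The test serves the primary objective in section 2, which is to identify relevant and modifiable perioperative risk factors. Section 3 says the factors found will be given optimum values and will shape the questionnaire for the follow-up study.

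The cohort is broad. Sections 4.1 to 4.3 admit benign and malignant disease, any anastomosis and ASA 1 to 3, with no exclusion criteria. On centres, section 3 says: "At the moment there is participation of seventeen hospitals in the Netherlands".

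Preoperative risk is recorded. Section 3 says of the screening: "This will be done by using the colon leakage score". Table 2 also records operation, anastomosis, elective status, stoma and hospital. None of these is given a role in the analysis.

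**The concern.** In an observational cohort, a crude test of deviation against leakage answers whether the two occur together. The primary objective asks something narrower: which intraoperative parameters are modifiable risk factors. Blood loss, inotropic use, MAP, fluid balance and glucose plausibly differ by patient risk and by type of operation. The Introduction itself accepts that preoperative factors predict leakage. A crude chi-squared test cannot tell a factor worth correcting from a marker of a sicker patient or a harder operation.

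At stake is the content of the follow-up checklist. A factor flagged only because it travels with case mix could become an optimisation target although correcting it would not lower the leak rate.

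**Working it through.** The documents give no error rate for this analysis, so there is no figure of the plan to reproduce. The question is how often the stated test flags a parameter with no effect.

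**Inputs from the Protocol**
- N = 2000 (sections 4.1 and 4.4).
- Alpha 0.05. It appears only in section 4.4; two-sided use for each parameter is my assumption.
- Leakage incidence 8% to 13% (Introduction).

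**Inputs assumed, because the documents give none**
- A share q = 0.30 of patients is high risk.
- Leak rates r1 (high risk) and r0 (others) are either 13% vs 8%, using the ends of the incidence range as two strata, or 15% vs 5%.
- The parameter deviates in f0 = 20% of the others and in f1 = 30%, 40% or 50% of high-risk patients. Within each stratum it has no effect on leakage.

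**Formulas**
- Share deviating: p = q·f1 + (1−q)·f0
- Leak rate if deviating: L1 = [q·f1·r1 + (1−q)·f0·r0] / p
- Leak rate if not deviating: L0 = [q·(1−f1)·r1 + (1−q)·(1−f0)·r0] / (1−p)
- Chance of p<0.05: Φ((d − 1.96·SE0)/SE1) + Φ((−d − 1.96·SE0)/SE1), where d = L1 − L0, SE0 is the pooled and SE1 the unpooled standard error.

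**Worked case, 15% vs 5%, f1 = 40%**
- p = 0.12 + 0.14 = 0.26, so 520 patients deviate and 1480 do not.
- L1 = (0.12×0.15 + 0.14×0.05)/0.26 = 0.0962
- L0 = (0.18×0.15 + 0.56×0.05)/0.74 = 0.0743, so the crude risk ratio is 1.29.
- SE0 = 0.0138 and SE1 = 0.0146. The chance of being flagged is 0.36.

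**Worked case, 13% vs 8%, f1 = 40%**
- L1 = (0.12×0.13 + 0.14×0.08)/0.26 = 0.1031
- L0 = (0.18×0.13 + 0.56×0.08)/0.74 = 0.0922, so the crude risk ratio is 1.12.
- SE0 = 0.0150 and SE1 = 0.0153. The chance of being flagged is 0.12.

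| Deviation, high risk vs others | Flagged, leak 13% vs 8% | Flagged, leak 15% vs 5% |
|---|---|---|
| 20% vs 20% (no confounding) | 5% | 5% |
| 30% vs 20% | 7% | 14% |
| 40% vs 20% | 12% | 36% |
| 50% vs 20% | 19% | 62% |

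The first row returns the nominal level, so the excess in the other rows comes from confounding.

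**Does stratification remove it?** In simulations of 2000 patients in 17 hospitals, a Mantel-Haenszel test stratified by risk group and hospital was set against the crude test, again for a null parameter. With leak 13% vs 8% and deviation 60% vs 30%, the crude test flagged 17.8% and the stratified test 4.7%. With leak 12% vs 4% and deviation 50% vs 30%, the figures were 26.4% and 6.3%.

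**Hospital alone.** With no case-mix effect and independent hospital variation in leakage and in the parameter (log-odds SD 0.3 and 0.7), the crude test flagged 4.8%. With SDs of 0.5 and 1.0 it flagged 10.3%, against 6.0% when stratified.

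**Number of tests.** Table 2 shows 19 legible items: 5 general condition, 5 perfusion, 1 contamination and 8 surgery related. Setting aside hospital, operation, elective status, anastomosis and stoma leaves 14. If all 14 were null, independent and tested at 0.05, the chance of at least one false positive would be 1 − 0.95^14 = 51%.

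**Events available.** 2000 × 8% = 160 and 2000 × 13% = 260. At the 8% and 2% of section 4.4 with equal groups, 1000 × 8% + 1000 × 2% = 100.

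**The case against.** The strongest reply is that covariates and multiplicity rules usually belong in a statistical analysis plan, which is not at hand. That would answer a complaint about missing detail. It does not answer this one, because the Protocol itself names the test for its primary objective, and the test it names is crude.

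Several other objections stand and limit the point.

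- A reader might infer that marker parameters will be declared risk factors. The documents do not support that. In most of the scenarios in the table a null parameter is flagged in well under half of studies, and every case-mix input is assumed.
- A reader might put hospital differences on a par with case mix. In the simulations they added little on their own.
- Urgency is a weaker confounder than it looks. Section 3 selects from weekly scheduled lists, and section 7.2 requires outpatient contact and a 24-hour interval before consent. Most emergencies could not enter this way, although Table 2 keeps an elective item.
- Counting all 19 items of Table 2 gives 1 − 0.95^19 = 62%, but about five of them are the natural adjusters and the extracted table has merged cells. Even the 51% for 14 needs independent tests and no true effects, whereas section 5.2 says the items were chosen for predictive value. No threshold per parameter is stated, and section 4.2 calls the project exploratory.
- The test result is not the only filter. Section 3 also asks that factors in the new questionnaire be frequently abnormal and modifiable, and compares values with the literature. Neither filter removes confounding, since a case-mix marker can be both.

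Two neighbouring matters are separate. The main parameter ("Main parameter is number of CAL patients with deviating perioperative risk factors") is a question of endpoint definition. For the secondary objective "Creating a profile identifying high risk patients perioperatively", the Protocol does not say that chi-squared tests will be used.

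**Conclusion.** The point holds in a limited form. As written, the analysis for the primary objective is a crude test in a heterogeneous observational cohort, and it can mistake a marker of case mix for a risk factor. Under the assumptions shown, a null parameter is flagged about 7% to 62% of the time instead of 5%, with central cases of 12% and 36%. The direction is secure, but the size is not, because the documents give neither the leak gradient between risk groups nor how deviations vary with risk. Multiplicity is a secondary matter. The change is still worth requiring, because it concerns the primary conclusion and much of the information needed for adjustment is already recorded.

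**What to change.** Replace the chi-squared sentence in section 3 and extend section 6.1 as follows.

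- The outcome is CAL (yes/no) by the Protocol's definition.
- For each candidate intraoperative parameter (about 14 legible in Table 2), the primary analysis is a logistic model for CAL with a hospital random intercept. It is adjusted for preoperative risk (the colon leakage score or its components), operation or anastomosis type, and elective status.
- Report adjusted odds ratios with 95% confidence intervals.
- State a multiplicity rule across the candidates, such as false discovery rate control, or label the results exploratory.
- Keep the chi-squared tests as description.

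The cost is mainly analysis wording, plus somewhat wider intervals. With about 100 to 260 leaks expected, and possibly fewer once section 3's rule of more than 90% checklist completion is applied, the covariate set must be small and fixed in advance. Two details need checking first. The title of the reference cited for the colon leakage score refers to left-sided surgery, so its components may suit the whole cohort better than the total. Table 2 lists the anastomosis without saying whether its site is recorded. Adjustment deals only with measured case mix, and the report should say so.
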